#### **8.4 Detection of Bias**

This is a randomized, active-controlled, double-blind and double-dummy study. Subjects will be stratified by screening serum PTH level (< 900 pg/mL, ≥ 900 pg/mL), screening serum cCa (< 9.0 mg/dL, ≥ 9.0 mg/dL) measured by central laboratory, and country (China and non-China), and be randomized 1:1 to receive etelcalcetide or cinacalcet. Blinding and randomization minimize bias. It is not expected that any study conduct procedures or statistical analysis will incur bias in the study results or conclusions. The potential sources of bias in this study are:

- a) Inadvertent breaking of the blind

Break of blind should be rare and anticipated only if it is necessary for safety and treatment reasons. Should this happen in more than 5% of the subjects in the study, a sensitivity analysis may be conducted for the primary endpoint by excluding those patients who were unblinded.

- b) Withdrawal

If there is a differential dropout rate between the treatment groups over the course of the study, the sensitivity of the conclusions on the primary and secondary endpoints due to drop out will be explored.

- c) Protocol deviations

A subject list of important protocol deviations will be finalized prior to the database lock and unblinding. The impact of protocol deviations on the study results will be investigated and a sensitivity analysis may be conducted if deemed necessary by

comparing the results of the primary endpoint analysis on subjects with and without protocol deviations.

Should any sensitivity analyses be required for potential bias in the study results and conclusions, the source and results of the sensitivity analyses will be documented in the CSR.

### **8.5 Outliers**

Various methods, including univariate summaries, histograms, scatter plots, box plots, and line graphs, may be used to identify outliers in key safety and efficacy variables.

Extreme data points will be identified during the blinded review of the data prior to database lock. Such data points will be reviewed with CDM to ensure accuracy.

Extreme data points will be included in the analyses.

Pharmacokinetic (PK) concentration data will be evaluated for outliers by visual inspection, and decisions to re-assay individual samples will be made in accordance with standard pharmacokinetic evaluation practice.

### **8.6 Distributional Characteristics**

The percent change endpoints will be analyzed using a repeated measures mixed effects model, which assumes that the data are normally distributed. The normality assumption will be assessed using the graphical methods such as the normal quantile-quantile plot (Q-Q plot) along with the Shapiro-Wilk test. If the normality assumption does not hold, data transformation will be considered.

### **8.7 Validation of Statistical Analyses**

Programs will be developed and maintained, and output will be verified in accordance with current risk-based quality control procedures.

Tables and listings will be produced with validated standard macro programs where standard macros can produce the specified outputs.

The production environment for statistical analyses consists of Amgen-supported versions of statistical analysis software; for example, the SAS System version 9.4.

## **9. Statistical Methods of Analysis**

### **9.1 General Considerations**

This is a phase 3 study to evaluate the efficacy of etelcalcetide as compared to cinacalcet. The primary objective is to determine if etelcalcetide is non-inferior to cinacalcet on achievement of a > 30% reduction from baseline in mean predialysis serum PTH during the EAP. Etelcalcetide will be considered non-inferior if the upper

bound of the two-sided 95% CI of the treatment difference (cinacalcet – etelcalcetide) is smaller than 12%. If this criterion is met, the 2 key secondary endpoints will be tested sequentially. The testing for the endpoint of achievement of a > 50% reduction from baseline in mean predialysis serum PTH during the EAP will be carried out first. Only if the result achieves statistical significance, the secondary endpoint of achievement of a > 30% reduction from baseline in mean predialysis serum PTH during the EAP will be tested. The other secondary endpoints will be formally tested for superiority if both key secondary endpoints are statistically significant. To control for the family-wise error rate, the Hochberg procedure of adjustment for multiple comparisons will be used for testing of the other secondary endpoints. The primary analysis of all primary and secondary endpoints will be conducted on the FAS.

For the efficacy endpoints using laboratory measurements (predialysis PTH, cCa, and P), values based on averaging over the EAP will be used in the analyses where applicable.

Baseline values for PTH, cCa, and P will be based on the mean of the last screening value and the day 1 value.

For analyses performed on cCa and Ca, only central laboratory results will be used.

Descriptive statistics include number of observations (n), mean, standard deviation (SD) or standard error (SE), median, 1st (Q1) and 3rd (Q3) quartiles, minimum and maximum will be used to summarize continuous variables. The number and percent of subjects will be used to summarize the categorical variables.

## **9.2 Subject Accountability**

The number (percentage) of subjects randomized, received IP, completed IP, and completed the study will be summarized by randomized treatment group based on the FAS. Reasons for study discontinuation and IP discontinuation will also be summarized separately by randomized treatment group.

Key study dates for the first subject enrolled, last subject enrolled, last subject's end of study, and last subject's end of IP will be presented.

## **9.3 Important Protocol Deviations**

Important Protocol Deviations (IPDs) categories are defined by the study team before the first subject's initial visit and updated during the IPD reviews throughout the study prior to database lock. These definitions of IPD categories, subcategory codes, and descriptions will be used during the course of the study. Eligibility deviations are defined

in the protocol. A table and a list of eligibility deviations will be generated for the Full Analysis Set.

#### **9.4 Demographic and Baseline Characteristics**

The following demographic and baseline characteristic will be summarized by treatment group and overall using descriptive statistics based on the FAS.

Sex, age, weight, height, BMI, race, ethnicity, stratification factors, iPTH, corrected total serum calcium, serum phosphorous, cCa x P, vital signs, selected concomitant medications, and selected medical history (history of hemodialysis, parathyroidectomy history, ESRD history, cardiovascular/social/other history).

#### **9.5 Efficacy Analyses**

All analyses of efficacy endpoints will be performed according to their randomized treatment group. The analyses of primary efficacy endpoint and key secondary efficacy endpoint are summarized in the following table and subsequent sections.

**Table 9-1. Primary and Key Secondary Endpoints Summary Table**

Endpoint	Primary Summary and Analysis Method	Sensitivity Analysis
Primary Endpoint		
Achievement of a > 30% reduction from baseline in mean predialysis serum PTH level during the efficacy assessment phase (EAP) (non-inferiority)	Mantel-Haenszel (M-H) estimation method adjusting for the three randomization stratification factors to estimate 95% CI based on the FAS. Multiple imputation under the non-inferiority null method will be applied to the subjects who do not have data during the EAP.	

1. iPTH Completer Case analysis (PCAS): similar to primary analysis method but only subjects who meet the criteria for inclusion in the PCAS are included.

2. Last value carried forward (LVCF): similar to primary analysis but using LVCF to impute missing data during the EAP. For subjects without PTH data during the EAP, the mean of the last 2 pre-dialysis PTH values obtained after Study Day 1 will be carried forward. If only one value is available, this single value will be carried forward to the EAP. A similar imputation approach as the primary analysis (non-inferiority null method) will be applied to subjects without a post-baseline PTH value after applying LVCF approach.

3. Per Protocol: similar as primary analysis method but using PPAS.

Page 1 of 2

**Table 9-1. Primary and Key Secondary Endpoints Summary Table**

Endpoint	Primary Summary and Analysis Method	Sensitivity Analysis
Key Secondary Endpoints		
Achievement of a > 50% reduction from baseline in mean predialysis serum PTH during the EAP (superiority)	A Cochran-Mantel-Haenszel (CMH) test adjusting for the three randomization stratification factors based on FAS. Subjects will be considered as not achieving the endpoint if they do not have data during the EAP (non-responder imputation).	Multiple Imputation (MI): for subjects without PTH data during the EAP, the multiple imputation method using SAS® PROC MI will be used to impute the PTH value during EAP. Treatment group, stratification factors, baseline covariates (as detailed in Section 4.1 ) will be considered for inclusion in the model as auxiliary variables. Full Analysis Set will be used for the analysis.
Achievement of a > 30% reduction from baseline in mean predialysis serum PTH during the EAP (superiority)	A Cochran-Mantel-Haenszel (CMH) test adjusting for the three randomization stratification factors based on FAS. Subjects will be considered as not achieving the endpoint if they do not have data during the EAP (ie. non-responder imputation).	Multiple Imputation (MI): for subjects without PTH data during the EAP, the multiple imputation method using SAS® PROC MI will be used to impute the PTH value during EAP. Treatment group, stratification factors, baseline covariates (as detailed in Section 4.1 ) will be considered for inclusion in the model as auxiliary variables. Full Analysis Set will be used for the analysis.

Page 2 of 2

### **9.5.1 Analyses of Primary Efficacy Endpoint(s)**

The analysis of the primary efficacy endpoint is to assess if the treatment of SHPT with etelcalcetide is not inferior to treatment with cinacalcet as measured by the proportion of subjects with > 30% reduction from baseline in mean predialysis serum PTH level during the EAP. Etelcalcetide will be considered non-inferior to cinacalcet if the upper bound of the two-sided 95% confidence interval of the treatment difference (cinacalcet - etelcalcetide) is smaller than 12%.

#### **9.5.1.1 Primary Analysis**

The primary endpoint will be analyzed using Mantel-Haenszel (M-H) estimation method [[Agresti and Hartzel, 2000](#)] stratified by screening PTH level (< 900 pg/mL, ≥ 900 pg/mL), screening serum cCa (< 9.0 mg/dL, ≥ 9.0 mg/dL) measured by the central laboratory, and country (China versus non-China) based on the FAS. The M-H estimator will be used to estimate the difference in the proportion of subjects who achieve the primary efficacy endpoint between two treatment groups and the standard error of the M-H estimator will also be estimated. The 95% two-sided confidence interval will be provided.

For the subjects who have at least one PTH value during EAP, the available data will be used to calculate the mean. For the subjects who have no PTH values during EAP, including subjects who discontinue the study, the missing primary endpoint will be imputed using non-inferiority null method [Koch, 2008]. The presumed response rate is 60% for the cinacalcet group. This response rate is based on the assumption that the cinacalcet group in study 20120360 resembles that studied in a previous cinacalcet clinical trial (Amgen EVOLVE trial 20050182) in which a response rate of 60% was observed for this endpoint in the cinacalcet arm. The response rate for the etecalcetide group is assumed to be 12% lower than that of the cinacalcet group (ie, 48%), with 12% being the pre-specified non-inferiority margin [Koch, 2008]. The imputation will be performed 5 times. The combination of estimating result for the M-H estimator and its standard error from each imputed data set will follow the method used in SAS® PROC MIANALYZE.

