An additional phase 3 study (20120360) was performed to compare the therapeutic efficacy of etelcalcetide and cinacalcet for lowering serum PTH concentrations among subjects with CKD and SHPT receiving maintenance hemodialysis. A higher observed percentage of subjects in the etelcalcetide group (77.9%) had a > 30% reduction from baseline in serum PTH during the EAP compared with the cinacalcet group (63.9%). The estimated treatment difference (cinacalcet - etelcalcetide) was -10.48% (95% confidence interval [CI]: -17.45%, -3.51%). Because the upper bound of the 95% CI is < 12% (the prespecified margin for noninferiority), etelcalcetide is noninferior to cinacalcet in the proportion of subjects with a > 30% reduction from baseline in serum PTH during the EAP. Additionally, etelcalcetide was superior to cinacalcet on the proportion of subjects achieving a > 50% and a > 30% reduction from baseline in mean predialysis serum PTH during the EAP. There was no significant difference in the mean number of days of vomiting or nausea per week in the first 8 weeks of treatment, as

Approved

measured by a patient-reported outcome instrument. The most common (> 10% in either treatment group) adverse events (etelcalcetide, cinacalcet) were asymptomatic decreased blood calcium (68.9%, 59.8%), nausea (18.3%, 22.6%), vomiting (13.3%, 13.8%), and diarrhea (6.2%, 10.3%). Symptomatic hypocalcemia was reported for 17 subjects (5.0%) in the etelcalcetide group and 8 subjects (2.3%) in the cinacalcet group.

Please refer to the etelcalcetide [Amgen Investigator Brochure](#) for additional detailed information about the chemistry, toxicology, preclinical pharmacology, pharmacokinetics (PK), safety, and clinical experience of etelcalcetide.

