### 3.2 Sample Size

The planned sample size is 660 subjects (330 subjects per treatment arm).

The sample size calculations are based on the results of the global head-to-head study (20120360) and take into consideration sufficient power for both the primary and secondary endpoints. The non-inferiority margin is defined based on results from EVOLVE trial (Amgen Study 20050182), which was a randomized, placebo-controlled trial. Using a similar subject population in the EVOLVE trial as intended to be recruited in this study, rates of 25% and 60% in the placebo and cinacalcet arms, respectively, achieved  $> 30\%$  reduction from baseline in iPTH at week 28 and the two-sided 95% CI

for the treatment difference based on the large sample normal approximation is (31%, 39%). Half of the lower limit of the CI for the treatment difference (compared to placebo) is 15.5%. Taking a conservative approach, the non-inferiority margin is defined as 12%.

Based on the global head-to-head study comparing etelcalcetide with cinacalcet (20120360), 58% of subjects randomized to cinacalcet and 68% of subjects randomized to etelcalcetide achieved a > 30% reduction from baseline in mean predialysis PTH during the EAP. Using this data, 300 subjects per treatment arm will provide over 99% power to demonstrate non-inferiority using a margin of 12% for the upper bound of the 95% 2-sided CI for the treatment difference between cinacalcet and etelcalcetide (cinacalcet - etelcalcetide).

For the key secondary endpoint of achievement of > 50% reduction from baseline in mean predialysis PTH during the EAP, 300 subjects per treatment group will provide approximately 84% power to detect a statistically significant difference between the treatment groups at the 5% significance level (two-sided), assuming a 52% and 40% response rate in subjects randomized to etelcalcetide and cinacalcet, respectively.

For the key secondary endpoint of achievement of > 30% reduction from baseline in mean predialysis PTH during the EAP (superiority analysis), 300 subjects per treatment group will provide about 72% power to detect a statistically significant difference between the treatment groups at the 5% significance level (two-sided), assuming a 68% and 58% response rate in subjects randomized to etelcalcetide and cinacalcet, respectively.

Considering the 10% dropout rate, the estimated sample size in each group is 330 subjects.

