### **6.3 Per Protocol Set(s)**

The Per Protocol Analysis Set (PPAS) is defined as all randomized subjects who have no major protocol violations (as defined below) and have at least one post-dose PTH value and had at least 16 weeks exposure of IP. Subjects with the following eligibility deviations will be excluded from the PPAS:

- Less than 18 years at screening
- Not receiving maintenance hemodialysis three times a week for at least 3 months
- Not meeting either calcium concentration or PTH eligibility criteria at screening
- Received cinacalcet within 3 months prior to screening or underwent a parathyroidectomy within 6 months prior to dosing
- Currently enrolling in another study or less than 30 days since ending another study
- Having known sensitivity to either cinacalcet or etelcalcetide

Moreover, subjects who have the following deviations during study period will also be excluded in this analysis set:

- Had parathyroidectomy or kidney transplant before EAP
- Received commercialized cinacalcet during the study
- Missed > 14 consecutive days of intravenous (IV) IP or oral IP, excluding the withholding of IP for protocol-specific reasons

For the subjects who undergo parathyroidectomy or kidney transplantation during EAP, only the PTH values before the surgery will be used.

Subjects in the PPAS will be analyzed according to randomized treatment assignment. PPAS will be used in the sensitivity analysis of the primary endpoint.

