#### **9.5.1.2 Sensitivity Analysis**

The following sensitivity analyses will be conducted using the same M-H method as in primary analysis:

- PCAS: similar to primary analysis method but only subjects who meet the criteria for inclusion in the PCAS are included.
- LVCF: similar as primary analysis method but using LVCF to impute missing data during the EAP. For subjects without PTH data during the EAP, the mean of the last 2 pre-dialysis PTH values obtained after Study Day 1 will be carried forward. If only one value is available, this single value will be carried forward to the EAP. The same imputation strategy for primary analysis will be employed for subjects without a post baseline PTH value.
- PPAS: similar as primary analysis method but only the subjects who meet the criteria for inclusion in the PPAS are included.

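### The primary non-inferiority imputation uses only 5 data sets, so the deciding upper bound carries avoidable seed noise (SD about 0.65 points at 10% missing); 100 or more would cut it to 0.13 at almost no cost

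*SAP*

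**What the plan says.** SAP 9.5.1 sets the decision rule: "Etelcalcetide will be considered non-inferior to cinacalcet if the upper bound of the two-sided 95% confidence interval" of the difference (cinacalcet minus etelcalcetide) is below 12%.

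SAP 9.5.1.1 estimates that difference by the Mantel-Haenszel (M-H) method over the three stratification factors in the full analysis set. Subjects with at least one PTH value in weeks 20 to 27 use their own data. The rest are imputed under the non-inferiority null, at 60% in the cinacalcet arm and 48% in the etelcalcetide arm. "The imputation will be performed 5 times", and the estimates are pooled as in PROC MIANALYZE.

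No reason is given for choosing 5. The SAP text available for review gives no seed, but it passes from the Section 12 heading straight to Appendix C, so a seed may be stated in pages that are not shown.

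SAP 9.5.1.2 reuses the imputation in the last-value-carried-forward (LVCF) analysis ("The same imputation strategy for primary analysis will be employed for subjects without a post baseline PTH value") and in the per-protocol analysis.

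**The concern.** The imputed outcomes are coin tosses at fixed rates. Averaging over 5 sets of tosses leaves Monte Carlo error in the estimate, in its between-imputation variance and in the degrees of freedom of the t reference. All three feed the one number that is compared with a fixed 12%. Two analysts following the same SAP on the same data could therefore report different bounds and, if the result were close, opposite primary conclusions. The primary test also gates both key secondary tests (SAP 9.5.2), and these gate the other secondary endpoints (SAP 9.1), so a failure caused by the seed would close the whole testing sequence.

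**Working it through.** **The plan's own figure.** SAP 3.2 claims over 99% non-inferiority power with 300 per arm, from "58% of subjects randomized to cinacalcet and 68% of subjects randomized to etelcalcetide" responding. With the unpooled normal approximation:

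Φ[(0.12 + 0.10) / √(0.58×0.42/300 + 0.68×0.32/300) − 1.96] = 99.99%.

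The stated power is reproduced. The documents give no figure for seed error.

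**Inputs.** 330 per arm; imputation rates 0.60 and 0.48; M = 5; Rubin's rules with t reference (SAP 3.2 and 9.5.1.1). The missing rate is an assumption, 10% or 33 per arm, taken from SAP 3.2: "Considering the 10% dropout rate, the estimated sample size in each group is 330 subjects".

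**Analytic check, point estimate.** With the observed data held fixed, the between-imputation variance is

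B = 33 × (0.60×0.40 + 0.48×0.52) / 330² = 33 × 0.4896 / 108,900, so √B = 1.22 points.

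The seed SD of the pooled difference is √(B/M): 1.22/√5 = 0.54 points at M = 5 and 1.22/√100 = 0.12 at M = 100.

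**Simulation, upper bound.** Observed data were fixed and only the seed varied. The bound is noisier than the point estimate because its standard error and t quantile vary too.

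| Missing per arm | M = 5 | M = 20 | M = 100 | M = 500 |
|---|---|---|---|---|
| 5% | 0.41 | – | 0.09 | – |
| 10% | 0.64 to 0.66 | 0.30 | 0.13 | 0.06 |
| 15% | 0.85 to 0.87 | – | 0.17 | – |
| 20% | 1.04 to 1.08 | – | 0.20 | – |

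Entries are seed SDs in percentage points. Repeating the 10% row with the 8-stratum M-H estimator (assumed strata sizes) gives 0.64 to 0.66, 0.13 and 0.06 at M = 5, 100 and 500, so stratification does not remove the noise.

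**Distance from 12% at the planning effect (10% missing, M = 5).**
- 68% v 58% among observed subjects: the bound averages 0.0%, with 95% of seeds between −1.2% and 1.3%.
- 77.9% v 63.9%, the rates that Protocol 2.2.1 reports for the same earlier study: the bound averages −3.7%, with 95% of seeds between −5.0% and −2.4%.

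No seed reached 12% in either case.

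**Is 10% plausible?** Suppose 68% and 58% count missing subjects as failures, and 77.9% and 63.9% are rates among observed subjects. Then missing is 1 − 0.68/0.779 = 12.7% for etelcalcetide and 1 − 0.58/0.639 = 9.2% for cinacalcet. Imputing these at 48% and 60% gives

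(0.58 + 0.0923×0.60) − (0.68 + 0.1271×0.48) = 0.6354 − 0.7410 = −10.56%.

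Protocol 2.2.1 reports: "The estimated treatment difference (cinacalcet - etelcalcetide) was -10.48"%. This supports the assumption but is inference. At these fractions the seed SD is 0.69 to 0.70 at M = 5 and 0.14 at M = 100.

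**A close result.** Take 178/297 cinacalcet and 169/297 etelcalcetide responders observed (60% v 57%), with 33 missing per arm. With unlimited imputations:
- cinacalcet (178 + 33×0.60)/330 = 59.94%; etelcalcetide (169 + 33×0.48)/330 = 56.01%; difference 3.93 points;
- total SE √(3.84² + 1.22²) = 4.03 points;
- upper bound 3.93 + 1.96×4.03 = 11.8%, which passes.

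At M = 5 the bound averages 11.92%, with 95% of seeds between 10.7% and 13.2%, and only about 55% of seeds pass. At M = 100 it averages 11.83% and about 90% pass. At M = 500 over 99% pass. The drop of about 0.1 point in the average comes from the smaller (1 + 1/M) variance term and t quantile, so the gain in pass rate is not all reduced noise.

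**Whole trials (10% missing at random, two seeds per trial).** Two seeds disagree on the verdict in 0.00% (77.9% v 63.9%) to 0.03% (68% v 58%) of trials at the planning effect. Outside the design assumptions, across separate runs at M = 5, they disagree in 5.7% to 6.2% (60% v 60%) and 7.5% to 7.9% (57% v 60%). At M = 100 these fall to 1.2% to 1.3% and 1.6% to 1.7%.

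**The case against.** Five imputations are not a defect. The method is fully specified, and the t reference allows for the small M. Operating characteristics barely move between M = 5 and M = 100: the pass rate is about 1.6% v 1.4% at a true 12-point deficit (nominal 2.5%), 51.3% v 52.0% at 57% v 60%, and 78.5% v 79.0% at 60% v 60%. At the planning effect it does not change. Disagreement between seeds becomes visible only when etelcalcetide is no better than cinacalcet, against the earlier evidence. A seed fixed in advance would by itself stop two analysts from differing, and one may exist in pages not shown. Missing PTH may also be rarer than dropout, because a single value in weeks 20 to 27 avoids imputation and assessments can continue off drug.

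All of this stands, and it is why the point is minor. It gives no reason to keep 5. A fixed seed makes the bound repeatable, but at M = 5 the bound would still depend on an arbitrary draw. Even at 5% missing the seed SD is 0.41 points. The figure of 100 is a judgement about adequate precision; it is not derived from a formal criterion.

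**Conclusion.** The point holds as a minor, almost free improvement. At 330 per arm and 10% missing, M = 5 gives the deciding bound a seed SD of about 0.65 points, against 0.13 at M = 100 and 0.06 at M = 500. The pooled interval is valid, type I error is not inflated, and at the planning effect the seed cannot realistically change the verdict. It matters only for a bound within about 1.3 points (two SDs) of 12%. The size rests on the assumed missing rate and scales roughly with its square root.

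The sensitivity analyses are little affected. The per-protocol set requires that subjects "had at least 16 weeks exposure of IP", and LVCF imputes only those with no post-baseline PTH. At an assumed 1% to 2% missing, the seed SD at M = 5 is 0.16 to 0.26 points.

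**What to change.** In SAP 9.5.1.1, replace 5 imputations with at least 100, preferably 500, and state the seed or point to where it is fixed. Let the same setting carry over to the LVCF and per-protocol analyses in 9.5.1.2. The imputation rates, margin, estimator and pooling method stay as they are.

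The cost is a change of SAP wording and minutes of computing, since each imputation is a fixed-rate Bernoulli draw followed by a closed-form M-H estimate. Make the change before unblinding.
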